- In the event that a patient develops any symptoms that could be possibly related to SARS-CoV-2 infection at home or out of the office, the patient must immediately test themselves using the SARS-CoV-2 Home Test Kit that was given to them at enrollment or go to a facility that can perform an EUA approved Breath Test for SARS-CoV-2 infection.
- In the event a positive test from the SARS-CoV-2 Home Test Kit or EUA approved Breath Test for SARS-CoV-2 infection is recorded, the patient must go to a qualified testing center and receive a SARS-COV-2 RNA by RT-PCR nasal swab test. These include LabCorp or Quest Diagnostics or a location that uses one of these two labs for the analysis (e.g., CVS).
- A positive SARS-COV-2 RNA by RT-PCR test must be sent to a qualified genomics laboratory (LabCorp or Quest Diagnostics) for detailed virus analysis
- In the event that a patient tests positive for SARS-CoV-2 infection by SARS-COV-2 RNA by RT-PCR, the patient should be instructed to contact their oncology center immediately
- In the event that a patient tests positive for SARS COV-2 RNA by RT-PCR, the patient must have blood drawn for serum concentration of AZD7442, RBD-IgG antibody level and T-cell analysis in the office approximately 10

days after the patient reported a positive test or in whatever timeframe is the acceptable protocol for a positive patient returning safely to the office of the Investigator.

- In the event that a patient develops a SARS-CoV-2 infection with symptoms, the patient should be immediately treated in accordance with Investigator judgement. Such treatment should include the current standard of care for symptomatic SARS-CoV-2 positive infection depending upon availability of immediate treatment. Such patient will be followed until day 360 of the study with all study procedures and assessments.
- Automatic request for patient medical records, pharmacy fill/refill data and medical insurance claims data for all patients for the 12 months post-baseline will be sent and forwarded to MediMergent for analysis.

[figure not shown]
Schedule of Activities:

	Screening/ Day 1 Baseline	Day 2	Day 30	Day 60	Day 90	Day 120	Day 150	Day 180	Day 181	Day 210	Day 240	Day 270	Day 300	Day 330	Day 360
Visit Window (Days)		+5	± 5	± 5	± 5	± 5	± 5	± 5	± 5	± 5	± 5	± 5	± 5	± 5	± 5
Informed Consent	X														
Authorization for Release of Health Info	X														
Inclusion/ Exclusion	X														
CBC including Platelet Count (if necessary)	X														

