SARS-CoV-2 antigen test by nasal swab	X														
SARS-CoV-2 RBD- IgG Antibody level	X				X			X				X			X
T-Cell Assay			X							X					
AZD7442 Administration	X							X							
Baseline Survey	X														
QoL Surveys		X	X		X			X				X			X

Follow-up Patient Experience/COA Surveys		X	X	X	X	X	X	X	X	X	X	X	X	X	X
Serum Concentration of AZD7442			X		X			X				X			X
SARS-CoV-2 by RT-PCR if home test positive and/or symptomatic		NOTE: In the event that a patient tests positive for SARS COV-2 by RT-PCR at any time, the patient must have blood drawn for serum concentration of AZD7442, RBD-IgG antibody level and T-cell analysis in the office approximately 10 days after the patient reported a positive test or in whatever timeframe is the acceptable protocol for a positive patient returning safely to the office of the Investigator.													

10.0 Immunologic Sub-Study Activities	
10.1 Sub-Study Secretome Assay
 
IsoPlexis’ Single Cell Multiplex Secretome Assay application measures T-cell polyfunctionality (i.e., the number of cells secreting multiple cytokines). From these data, the Polyfunctional Strength Index (PSI) will be calculated as a numeric output generated as the product of T-cell polyfunctionality multiplied by the intensity of the measured signal using fluorescent imaging. These data generate functional information relating to:
 
 • CD4 T-cells (Helper T-cells) which produce cytokines to activate immune cells including B-cells, CD-8 T-cells and macrophages. • CD8 T-cells (Cytotoxic T-cells) which destroy virus-infected cells and tumor cells by either lysis and/or apoptosis. 
10.2 CD4 and CD8 T-Cell Function
 
In general, CD4 and CD8 T-cell function increases during active SARS-CoV-2 infection reflecting stimulation and activation of T-cell immune response. The magnitude of this increase in T-cell function appears to be related to the severity of COVID-19 disease. Specifically, previous data acquired in immunocompetent subjects have reported that CD4 and CD8 T-cell function significantly increase in response to active SARS-CoV-2 infection in subjects with mild-to-moderate SARS-CoV-2 disease. However, subjects with moderate or more severe SARS-CoV-2 disease may have a blunted T-cell response due to “exhaustion” of the cells’ ability to mount a sustained cellular immune response.

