14.1 Definitions and Secondary Endpoints

Definition of SARS-CoV-2 qualifying symptoms:

SARS-CoV-2 qualifying symptoms are based on the definitions in the AstraZeneca PROVENT trial. In combination with a positive SARS-CoV-2 antigen test, symptomatic infection includes at least one of the following symptoms and duration:

- No minimum duration
 - Fever, shortness of breath, difficulty breathing, new onset confusion (only for patients ≥ 60 years), appetite loss or decrease food intake (only for patients ≥ 60 years), increased supplemental oxygen requirement (only for patients ≥ 60 years on baseline supplemental oxygen)
- Must be present for ≥ 2 days
 - Chills, cough, fatigue, muscle aches, body aches, headache, new loss of taste, new loss of smell, sore throat, congestion, runny nose, nausea, vomiting, diarrhea

Secondary Endpoints will include the following:

- Incidence of symptomatic SARS-CoV-2 infections including but not limited to those with SARS-CoV-2 related hospitalization and/or SARS-CoV-2 related death compared between solid tumor and hematologic malignancy patients.
- Incidence of symptomatic SARS-CoV-2 infection including but not limited to SARS-CoV-2 related hospitalization and/or SARS-CoV-2 related death compared between patients treated with chemotherapy only, immunotherapy only, targeted therapy only or other/combination therapy only over 12 months post-baseline.
- Serum AZD7442 concentrations at 1, 3, 6, 9 and 12-months post-baseline compared between solid tumor and hematologic malignancy patients.
- Serum AZD7442 concentrations at 1, 3, 6, 9 and 12-months post-baseline compared between patients treated with chemotherapy only, immunotherapy only, targeted therapy only or other/combination therapy only.

- Correlation of the incidence of symptomatic SARS-CoV-2 infection including but not limited to those with SARS-CoV-2 related hospitalization and/or SARS-CoV-2 related death to the levels of serum concentration of AZD7442 at 1, 3, 6, 9 and 12-months post-baseline in all patients.
- Incidence of symptomatic SARS-CoV-2 infection including but not limited to SARS-CoV-2 related hospitalization and/or SARS-CoV-2 related death compared between patients currently on active treatment, ≤ 3 months post-treatment and > 3 months and ≤ 12 months post-treatment regardless of treatment strata.
- Incidence of Severe SARS-CoV-2 (pneumonia or hypoxemia) and WHO score of ≥ 5 compared between all four strata

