17.5 Missing Data

There are several potential missing data considerations within this study. These are outlined as follows with associated methods of handling the missing information.

- Serum AZD7442 concentration: For both the ITT and PP populations, if a patient has serum AZD7442 at Day 30 and Day 90 but does not have an additional timepoint at Day 180 then the value for the missing serum AZD7442 concentration data point at Day 180 will be predicted from the linear regression of the log

AZD7442 serum concentration from the Day 90 analysis. Otherwise, the missing AZD7442 serum concentration data will be treated as missing data.

- SARS-CoV-2 infection: Will be determined through the documentation of SARS-CoV-2 diagnosis either through SARS-CoV-2 by Rt-PCR test, the medical record or claims information. Multiple locations of documentation will be considered a confirmed diagnosis.

- Clinical Outcome Assessment/Quality of Life Assessment: If data are missing through the survey collection process, then only the relevant measures will be calculated. Appropriate consideration of missing values will be addressed for time points comparison either through the non-inclusion of the patient outcome in that time point and/or within regression model assessment.

- RBG-IgG antibody level: Correlations will be determined where there is complete information only.

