	
17.10 Breakthrough Infection Descriptive Analysis
 
All patients who experience a symptomatic breakthrough SARS-CoV-2 infection, defined as a positive SARS-COV-2 RNA by RT-PCR test with or without viral genomics and/or symptomatic clinical evidence of SARS-CoV-2 disease, will have a descriptive analysis that includes a clinical outcome (e.g., symptomatic infection, SARS-CoV-2 related hospitalization and/or SARS-CoV-2 related death), a profile of neutralizing antibody as measured by serum concentration of AZD7442, a functional analysis of T- characterized by cytokine stimulation and secretion and a genomic sequencing of the virus. In addition, relationship between these data and World Health Organization Ordinal Scale for Severity of SARS-CoV-2 Disease will be performed.
 
17.11 Patient Demographics, Disease and Treatment Attributes
 
Baseline patient characteristics for all enrolled participants include age, gender, race, weight and Body Mass Index (BMI) and will be analyzed using descriptive statistics for all strata and sub-strata. Patient demographics, disease and treatment attributes will be summarized and compared between the disease category cohorts and concomitant treatment regimens. Any attributes with significant differences will be considered for inclusion as factors in logistic regression and linear model analyses. Disease attributes will include stage of disease, time from initial diagnosis and performance status will be assessed. Treatment regimen attributes including type of therapy, cycle at time of study enrollment and cycle duration will be summarized.
 
17.12 Statistical Models
 
Statistical considerations for other endpoints will be treated on a case-by-case basis depending on the nature of the outcome variables and their distributions. Such approaches may include χ^2 cross-tabulations, t-tests, ANOVAs, negative-binomial regressions, logistic regressions, mixed model for repeated measures and linear regression.

18.0
	
18.1 Identification of Non-Serious and Serious Adverse Events

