18.6 Investigator Responsibilities

The Investigator and any qualified designees are responsible for detecting, documenting, and reporting events that meet the definition of an AE or SAE and remain responsible for following up AEs that are serious, considered related to the

	
study intervention or the study, or that caused the participant to discontinue the study. Data on hospitalization or death should additionally be recorded on the Safety Report Form, for all relevant sections. The method of recording, evaluating, and assessing causality of AEs and SAEs and the procedures for completing and transmitting SAE reports are provided in the Safety Reporting section of this document.
 
18.7 MediMergent Pharmacovigilance
 
The MediMergent Pharmacovigilance team will be responsible for oversight of all safety data and for determining the expectedness of all SAEs, expedited reporting of individual cases, and safety updates to regulatory authorities and AstraZeneca.

19.0 Quality of Life Data
	
19.1 Quality-of-Life Evaluations
 
All Quality-of-Life data will be derived from questions in the baseline (Day 2) and follow-up QoL assessments. Each response will be given a numeric value and the sum of all responses will serve as the QoL “score” for a given patient at a given timepoint. The scoring will be determined such that the higher the score, the better the QoL. The comparison for all patients will use a change from baseline model. Scores at each time point for all patients for a given dose and cancer type will generate a mean, SD and SEM. The change from baseline at each post-baseline timepoint will be compared using two-tailed t-test comparison with $P < .05$ as significant. The mean change from baseline will be compared for all cancer patients treated with AZD7442 600 mg IM or IV and then sub-divided by comparisons between chemotherapy only, immunotherapy only, targeted therapy only and other/combination therapy only.

20.0 Adjudication: Clinical Events Committee (CEC)
	
20.1 Clinical Events Committee Functionality
 
An independent Clinical Events Committee (CEC) will be assembled to adjudicate/evaluate using a pre-specified adjudication operations manual, all clinical events data associated with SARS-COV-2 RNA by RT-PCR positive symptomatic SARS-CoV-2 infection including SARS-CoV-2 infection relatedness and/or impact on hospitalizations and deaths. In addition, the CEC will use the available clinical

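### Symptomatic SARS-CoV-2 infection is classified differently in 1.1/14.1, 14.3 and 17.10, and 9.3 and the Schedule give different RT-PCR triggers, so secondary infection results depend on which section is followed

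*Protocol*

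**What the plan says.** Section 14.1, under the heading for definitions and secondary endpoints, repeats the rule in 1.1: "In combination with a positive SARS-CoV-2 antigen test, symptomatic infection includes at least one of the following symptoms and duration". The list that follows separates symptoms with no minimum duration from symptoms that must last at least two days. RT-PCR does not appear in this rule.

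Section 14.3 lists clinical outcomes for exploratory use and gives symptomatic infection, in parentheses, as the meaning of a positive RT-PCR test. It adds no symptom condition.

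Section 17.10 selects patients with symptomatic breakthrough infection, "defined as a positive SARS-COV-2 RNA by RT-PCR test with or without viral genomics and/or symptomatic clinical evidence of SARS-CoV-2 disease".

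Section 17.5 says how infection is established from the data: "Will be determined through the documentation of SARS-CoV-2 diagnosis either through SARS-CoV-2 by Rt-PCR test, the medical record or claims information". It continues: "Multiple locations of documentation will be considered a confirmed diagnosis". It does not say how a case with a single source is treated.

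On testing, 9.3 tells a patient with possible symptoms to use the home kit or go for a breath test. It then sets the condition for RT-PCR: "In the event a positive test from the SARS-CoV-2 Home Test Kit or EUA approved Breath Test for SARS-CoV-2 infection is recorded". The Schedule of Activities row reads: "SARS-CoV-2 by RT-PCR if home test positive and/or symptomatic".

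On adjudication, 20.1 gives the CEC "all clinical events data associated with SARS-COV-2 RNA by RT-PCR positive symptomatic SARS-CoV-2 infection". Section 25.22 gives it every potential event relating to symptomatic infection, with no RT-PCR condition.

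**The concern.** A case definition has to put each patient in the same category wherever the term is used. Here one label carries an antigen-based rule, an RT-PCR rule and an *and/or* rule, and no section says which one governs.

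Several secondary endpoints in 14.1 depend on the term: incidence by disease, by therapy stratum and by time since treatment; the symptomatic-infection component of time to first event; and the correlation of infection with serum concentration. The descriptive breakthrough analysis in 17.10 depends on it too. Symptomatic infection is also the subject of the primary clinical hypothesis in 2.1, so readers will look at these results closely.

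The two RT-PCR triggers add a separate problem. Up to 75 sites will be testing patients. If some follow 9.3 and others the Schedule, the chance that an infection is found depends on the site, and a test that was not done cannot be recovered at the analysis stage.

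**Working it through.** The protocol states no expected rate, sample size or power for symptomatic infection, so there is no figure of its own to reproduce. The check is logical: apply each rule to every combination of three yes/no facts.

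Inputs:
- 14.1 (same as 1.1): antigen positive AND qualifying symptom.
- 14.3: RT-PCR positive.
- 17.10 read as *or*: RT-PCR positive OR symptomatic clinical evidence.
- 17.10 read as *and*: RT-PCR positive AND symptomatic clinical evidence.

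Two simplifications: symptomatic clinical evidence in 17.10 is treated as equal to a 14.1 qualifying symptom, and a test not done counts as not positive.

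| Antigen + | RT-PCR + | Symptom | 14.1 | 14.3 | 17.10 *or* | 17.10 *and* |
|---|---|---|---|---|---|---|
| no | no | no | no | no | no | no |
| no | no | yes | no | no | case | no |
| no | yes | no | no | case | case | no |
| no | yes | yes | no | case | case | case |
| yes | no | no | no | no | no | no |
| yes | no | yes | case | no | case | no |
| yes | yes | no | no | case | case | no |
| yes | yes | yes | case | case | case | case |

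Profiles counted as cases: 14.1, 2 of 8; 14.3, 4 of 8; 17.10, 6 of 8 as *or* and 2 of 8 as *and*. With 17.10 as *or*, the three rules disagree on rows 2, 3, 4, 6 and 7, which is 5 of 8. With 17.10 as *and*, they disagree on rows 3, 4, 6 and 7, which is 4 of 8. These count logical profiles, not expected patients.

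Row 4 arises from the protocol's own testing path. Section 9.3 lets a symptomatic patient take a breath test in place of the home kit and then go to RT-PCR. That patient can be symptomatic and RT-PCR positive with no antigen result: a case in 14.3 and in 17.10 on either reading, but not in 14.1. A symptomatic patient with a negative antigen test and a positive RT-PCR is classified the same way.

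Now take a symptomatic patient whose home test is negative. Under 9.3 no RT-PCR is called for; under the Schedule it is. If the home kit is an antigen test (the protocol does not say so), this patient is not a 14.1 case either way. Under 14.3, or 17.10 read as *and*, the patient is a case only if tested and positive. How much the trigger conflict matters therefore depends on which definition governs.

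Section 17.5 adds chart and claims as sources without linking them to the antigen test or symptoms in 14.1. Sections 20.1 and 25.22 describe two different sets of infection events for adjudication.

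**The case against.** The strongest reply is that 14.1 already governs. Its heading announces definitions, it introduces the secondary endpoints, and it repeats 1.1. Section 14.3 is exploratory and 17.10 is descriptive, and nothing applies the 17.10 wording to incidence or time to event. This limits the reach of 17.10 and makes 14.1 the natural candidate. It does not remove the conflict, because the protocol never says that 14.1 governs and the other two sections use the same term with a different meaning.

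One could also read antigen test in 14.1 loosely, since an exclusion criterion in 8.2 groups RT-PCR under antigen testing. Section 9.1, however, treats the tests as distinct and lets RT-PCR overrule the rapid antigen result. Even on the loose reading (either test positive, plus a symptom), only row 4 is resolved: rows 2, 3, 6 and 7 remain under *or* (4 of 8) and rows 3, 6 and 7 under *and* (3 of 8).

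The adjudication manual named in 20.1, or a statistical analysis plan, neither of which is at hand, may settle the definition for analysis. Neither can supply RT-PCR tests that a site did not do.

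Some stronger readings are tempting but not supported:
- That cases without RT-PCR never reach the CEC. Section 25.22 has no RT-PCR condition, and 18.5 and 25.3 send all acute-illness hospitalizations to it. The finding is only that the scope in 20.1 and 25.22 differs.
- That 17.5 is a further rival definition. It sits under missing data and concerns infection, not symptomatic infection; it is an ascertainment rule.
- That 17.10 counts any patient with fatigue or nausea. It asks for clinical evidence of SARS-CoV-2 disease, and 9.3 requires prompt self-testing or a breath test.
- That the machine-learning target shares the problem. In 14.1 and 22.1 that target is infection, without a symptom condition.

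**Conclusion.** The inconsistency is real and shows from the text alone: 1.1/14.1, 14.3 and 17.10 classify the same patient differently, and 9.3 and the Schedule differ on who has RT-PCR. It affects the secondary symptomatic-infection endpoints and the descriptive breakthrough analysis. The primary endpoint in 13.1, serum concentration, is unaffected.

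The size in patients cannot be computed. A reader might assume 15% incidence and 60–80% antigen sensitivity and obtain 1,500 × 0.15 = 225 cases, of which 225 × 0.20 = 45 to 225 × 0.40 = 90 would go without RT-PCR under 9.3. Neither assumption is in the protocol, the breath-test route is ignored, and under the antigen-based rule in 14.1 those patients are not cases whether or not they are tested. Nor do the documents show the direction of any bias: extra symptom-based cases could dilute differences between strata, or create them if symptoms vary with therapy.

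The conclusion rests on a literal reading of the sections. It survives either reading of *and/or* and the loose reading of antigen test.

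**What to change.** State one governing case definition for the secondary symptomatic-infection endpoints and use it in 1.1, 14.1, 14.3 and 17.10. One workable form is laboratory-confirmed infection, with the accepted test or tests named, AND at least one 14.1 qualifying symptom of the required duration, adjudicated by the CEC.

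- In 17.10, replace *and/or* with *and*.
- In 14.3, separate RT-PCR positivity from symptomatic infection, and report asymptomatic RT-PCR positives on their own.
- In 17.5, link the sources to the governing definition, state how single-source cases are treated, and place chart-only or claims-only cases in a sensitivity analysis.
- Give the CEC the same scope in 20.1 and 25.22.
- Reconcile the RT-PCR trigger in 9.3 with the Schedule so that all sites follow one rule. Which rule is for the sponsor and investigators to decide.

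The cost is wording changes and one additional sensitivity analysis. The trigger should be settled first, because it affects what data are collected.
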